 Exclusion criteria	14
Data collection techniques	16
Data Management and Statistical Analysis	16
Table of Variables	19
Blank Tables	23
OPERATIONAL ASPECTS	28
SOCIALIZATION OF RESULTS	29
ETHICAL CONSIDERATIONS	29
SCHEDULE	33
REFERENCES	35
ANNEXES	38

INTRODUCTION

The incidence of placenta accreta spectrum (PAS) has hiked up, directly proportional to the increased frequency of cesarean section (1). As the name implies, the condition includes a spectrum of various clinical presentations, from "mild" forms, which if managed by expert groups can have intraoperative risks similar to cesarean section; to very severe forms that can lead to death and require both great surgical skill and the use of multiple healthcare resources (2).

The classification of PAS adopted by the International Federation of Gynecologists (FIGO) is based on the degree of penetration of the placenta into the myometrium. Therefore, its histologic staging is only possible by analyzing a tissue sample after surgery and does not contribute to surgical decisions. In addition, histological analysis is seldom available in center with limited resources (3).

Among the characteristics expected to be found in a classification applied for a disease that is managed surgically, its application prior to surgery (based on imaging studies) and its confirmation during laparotomy, are ideal. Additionally, such a classification should make it easier to choose the treatment option and correlate with the clinical results or the degree of surgical difficulty. An interesting proposal for PAS is the topographic classification created by [name] et al (1), with 5 differentiated categories based on the part of the uterus affected and the possibility of separating or not the uterus from the bladder. This classification has been studied and successfully implemented by hospitals in low- and middle-income countries, and retrospective studies have been carried out describing its correlation with clinical results and the usefulness of one or another surgical technique (1,4). Currently there are no prospective multicentric studies that address the relationship between this anatomical classification with clinical variables, and no study has reviewed the opinions of the professionals who use it.

We propose the execution of a prospective multicentric study consisting of a cohort of patients with prenatal or intraoperative diagnosis of PAS, evaluating the clinical outcomes of the group of patients found in each category of the topographic classification. In addition, an approach to evaluate the acceptability of this classification among the obstetrician-gynecologists of the participating medical centers will be included.

THEORETICAL FRAMEWORK

Definition

Traditionally, PAS has been considered to be due to an abnormal insertion of the placenta, when the chorionic villi abnormally invade the myometrium (5). However, recent publications emphasize the non-invasive nature of placentation in PAS. The fundamental problem is the presence of an established myometrial defect in the uterus prior to pregnancy, clearly linked to previous surgical trauma, been history of cesarean section the main risk factor. When the placenta implants over that defect, as is the case of placenta previa in women with a history of cesarean section, abnormal migration of the placenta to deeper than usual planes in the uterine wall is possible (5). PAS is a severe complication of pregnancy associated with massive and life-threatening bleeding and has become one of the main causes of emergency hysterectomy (6).

Traditional classification

PAS has traditionally been classified based on the degree of penetration of the placenta into the myometrium (7). Therefore, only through the analysis of the post-hysterectomy uterus it's possible to know where the patient was classified into. Due of the limitations of the histology-based approach of the traditional classification, some clinical criteria have been included, obtained during the laparotomy, proposed by FIGO (7). Something similar has been previously described by Collins et al (8). Those findings are not necessarily related to surgical difficulty and expected bleeding volume. Some authors indicate that those kinds of findings can be observed even in the absence of PAS since they are present in cases of uterine dehiscence with placenta previa (9).

Table 1. General classification of PAS (FIGO)

Grade 1 Abnormally Adhered Placenta
	
Clinical criteria Vaginal delivery
 
 ● There is no separation with synthetic oxytocin and controlled cord traction.
---	--


(Adherent placenta or accreta).
	
 • Attempts of manual removal of the placenta result in profuse bleeding from the site of placental implantation, requiring mechanical maneuvers or surgical procedures. 
If laparotomy is required (even for cesarean delivery)
 
 • Same as above. • Macroscopically, the uterus shows no obvious distention over the placental bed ("placental protrusion"), no placental tissue invading the surface of the uterus, and nonexistent or minimal neovascularization. 
Histological criteria
 
 • Microscopic examinations of placental bed samples from a hysterectomy specimen shows wide areas of absent decidua between the villous tissue and the myometrium, with placental villi attached directly to the superficial myometrium. • The diagnosis cannot be made with freshly harvested placental tissue or random biopsies of the placental bed.

Grade 2 Abnormally invasive placenta (Increta).
	
Clinical criteria
 
At laparotomy
 
 • Abnormal gross findings on the placental bed: bluish/purple coloration, distension (placental "lump"). • Significant amounts of hypervascularization (dense vessels bed, convoluted vessels or multiple vessels running parallel and cephalocaudal along the uterine serosa). • No placental tissue is observed invading the uterine serosa. • Gentle cord traction causes the uterus to pull inward and there is no placental separation (the so-called dimple sign). 
Histological criteria.

	
 • Uterine sample from hysterectomy or partial myometrial resection of the increta area showing placental villi within the muscle fibers, and sometimes in the lumen of the deep uterine vasculature (radial or arcuate arteries).

Grade 3 Abnormally invasive placenta (Percreta).
	
Grade 3a: Limited to the uterine serosa
 
Clinical Criteria
 
In laparotomy
 
 • Abnormal gross findings on the uterine serosal surface (as noted above) and placental tissue has invaded the surface of the uterus. • No invasion of any other organ, the posterior wall of the bladder included (a clear surgical plane can be identified between the bladder and the uterus). 
Histological criteria
 
 • Uterine specimen from hysterectomy, showing villous tissue within or perforating the uterine serosa.
	
Grade 3b: Invasion of the bladder
 
Clinical Criteria
 
In laparotomy
 
 • Placental villi are observed invade the bladder, but not other organs. • No clear surgical plane can be identified between the bladder and the uterus. 
Histological criteria
 
 • Uterine specimen from hysterectomy showing villous tissue perforating the uterine serosa and invading the bladder wall or the urothelium.
	
Grade 3c: Invasion of other pelvic organs or tissues
 
Clinical Criteria
 
In laparotomy
 
 • Placental villi are found invading the broad ligament, the vaginal wall, the pelvic lateral wall

	
or any other pelvic organ (with or without invasion of the bladder).
 
Histological criteria
 
 • Uterine specimen from hysterectomy showing villous tissue perforating the uterine serosa and invading pelvic organs or tissues (with or without bladder invasion). 
For the purposes of this classification, "uterus" includes the uterine body and cervix.

--	--

In addition to the difficulties associated with the traditional classification, it does not provide an ideal route on how to manage each case. The management options for PAS are multiple (10,11), without concretely defining which strategy is superior to others. It is common for a hospital and its PAS expert group to choose one type of treatment option and specialize in it, applying it in almost all their cases despite the variability of clinical presentations of PAS. For example, some protocols include embolization before or after fetal extraction (12), others apply total (13) or subtotal (14) hysterectomy in all cases, and others prefer expectant management, leaving the placenta in situ and waiting for its expulsion or resorption after a few weeks (15).

The indiscriminated application of a specific procedure, exposes patients with less severe forms of PAS to the complications of that procedure (16), probably without gaining any additional benefit since they could have been managed with simpler interventions (2). Vascular management procedures (endovascular balloons, retroperitoneal dissection for aortic or internal iliac vessel clamping) have risks (17). Even total abdominal hysterectomy is associated with early ovarian failure and irreversible loss of fertility, along with psychological consequences for patients (18). Furthermore, it has been repeatedly demonstrated that hysterectomy is associated with greater blood loss, a higher rate of maternal complications and increased admission to intensive care for catastrophic bleeding (>2500 ml) compared to uterine sparing surgery (19).

Topographic classification

Due to the situation with the traditional classification, an interesting proposal rises, which is the topographic classification created by [name] et al (1). This classification considers which uterine wall is affected (anterior, posterior or lateral), in addition to the level of involvement of the uterus (above or below the vesicouterine peritoneal fold) (4).

It also includes knowledge of uterine irrigation and changes in pelvic anatomy when PAS is present, making it clear that lesions that occupy the lower part of the uterus, cervix or parametrium, known as sector 2 of uterine vascularization (1,20), present greater surgical difficulty. In this location, in addition to a complex anastomotic arterial network (vesical, vaginal, and cervical arteries, among others), there is proximity to urinary, nervous and vascular structures. Considering all the aforementioned conditions, the intraoperative findings define the category in which the patient is classified and recommendations for surgical management are established (**table 2**) (4).

Table 2. Topographic classification of Placenta Accreta Spectrum (21)

Type of PAS	Arterial pedicles		Vascular procedures	Proposed treatment
0	UA		None	OSCS
1	UA, SVA		NFV dissection/ligation	OSCS
2	2U Upper (Upper)	ObtA, IIA collaterals, UA, UretV	NFV dissection/ligation	OSCS
	2L Low (Lower)	IIA collaterals, CA, VA, UretV	IRAA, bilateral CIA	Total hysterectomy
3	SVA, IVA, UA, CA, VA, VA		NFV dissection/ligature IRAA, bilateral CIA	OSCS vs Total hysterectomy

4	SVA, IVA, UA, CA, VA, VA		IRAA, bilateral CIA	MSTH
5	5U Upper (Upper)	UA, OA, collateral flow from IMA, IMA fr om IMA	UA ligation	OSCS
	5L Low (Lower)	UA, ARA collaterals	IRAA	Total hysterectomy

Intraoperative staging makes it possible to determine which uterine wall is affected and the relationship of the lesion to the vesicouterine peritoneal fold (above or below that level), as well as the predominance of neovascularization or the presence of vesicouterine fibrosis.

In each topography, arterial pedicles are identified that provide most of the irrigation to the PAS area and determine the recommended vascular procedures and the type of treatment required (One Step Conservative Surgery [OSCS], Total Hysterectomy or Modified Subtotal Hysterectomy [MSTH]).

PAS type 0: uterine "window" or dehiscence. PAS type 1: involvement of the upper part of the uterine segment. PAS type 2: parametrial involvement (2A: upper parametrial involvement, 2B: lower parametrial involvement). PAS type 3: involvement of the cervix or lower uterine segment (below the peritoneal reflex). PAS type 4: PAS type 3 plus vesicouterine fibrosis. PAS type 5: Involvement of the posterior uterine wall (5A: Involvement of the upper part of the posterior uterine wall. 5B: Lesions below the level of the peritoneal reflexion).

AU: Uterine artery. **SVA:** Superior vesical artery. **NFV:** Neo-forming vessels. **ObtA:** obturator artery. **IIA:** internal iliac artery. **UretV:** ureteral vessels. **CA:** cervical artery. **VA:** vaginal arteries. **IVA:** inferior vesical artery. **OA:** ovarian artery. **IMA:** inferior mesenteric artery. **ARA:** anterior rectal artery. **IRAA:** infrarenal aortic artery. **ICA:** common iliac artery

Another key factor is that a significant percentage of the hospitals responsible for the management of PAS do not have extensive experience in the management of the disease, and there are very few centers with a high flow of cases per year (22,23). Many of the hospitals do not have all the technological resources recommended by the so-called "centers of excellence" in PAS, nor do they have teams dedicated solely to the management of this disease ("PAS teams") (24,25). Those hospitals face difficulties in

choosing which type of treatment to offer each PAS patient who consults. Thus, it is common for most hospitals organizing their PAS team for the first time, to decide to offer hysterectomy to all their patients, even in cases with prenatal diagnostic uncertainty. Many groups even choose to apply vascular interventions to all of their PAS patients, even if such interventions ultimately prove to be excessive for the type of lesion found during surgery.

This is worrisome, as 22% of the cases taken to hysterectomy for PAS do not end up having the diagnosis (26). This has become more relevant since it has been reported that most patients with PAS present with "mild" forms of the disease due to "superficial" penetration of the placenta into the uterine wall (13) or involvement of the upper part of the uterus, known as vascular sector 1 (1). All that without mentioning how when evaluating the perceptions of patients treated for PAS, they express how important it would have been to have options other than hysterectomy and to know that there was the possibility of preserving fertility in selected cases (27).

In centers using the PAS topographic classification and individualized surgical management according to the severity of the lesion, up to 80% of cases can be managed with uterine-sparing surgery without increasing the volume of blood loss (1). The PAS topographic classification has been used in retrospective studies in low- and middle-income countries (1,4) that correlates with clinical outcomes that justifies specific surgical interventions in selected cases. For example, it has been found that type 1 classification, which is the most frequent, is associated with less bleeding and a higher uterine preservation rate; while the types that include low parametrial invasion and invasion of the bladder trigone do not exceed 10% of cases and are linked to increased bleeding and higher surgical challenges (1).

It should be noted that the available literature describing the relationship between topographic classification and its correlation with clinical outcomes is scarce, so it is considered essential to evaluate this classification in a prospective multicentric study that assesses its validity and correlation to surgical difficulty and

clinical outcomes, which could determine the usefulness of the classification in the clinical setting.

JUSTIFICATION FOR THE STUDY

This research aims to evaluate the usefulness of the topographic classification of PAS. Although the classification is based on intraoperative findings and recognizes the particularities within each case of PAS, which has shown correlation to surgical difficulty and the effectiveness of one or another treatment option. To date there are no prospective multicentric studies that deepen and provide further strength to the above associations. In addition, the ease of its application and the acceptability of its use by the obstetrician-gynecologists physicians who use it, is yet unknown.

The topographic classification recognizes the pelvic anatomy and specially the arterial pedicles that irrigate each part of the uterus. It can be applied before incising the uterus and causing bleeding, enables a smooth decision-making process to choose the most appropriate surgical technique for each case, as well as the need for specific vascular interventions. Confirming its usefulness in different countries will facilitate its use by interdisciplinary teams dedicated to the management of PAS at the international level.

RESEARCH QUESTION

Is the topographic classification of placenta accreta spectrum useful in determining possible clinical outcomes? How acceptable it is by obstetrician-gynecologists who manage PAS?

RESEARCH HYPOTHESES

The topographic classification of placenta accreta spectrum is useful in determining possible clinical outcomes. The topographic classification has high acceptability among obstetrician-gynecologists who manage PAS.

OBJECTIVES

- *General*

To evaluate the clinical outcomes of patients with a diagnosis of placenta accreta spectrum according to the topographic classification, and to explore the acceptability of this classification among obstetrician-gynecologists at the participating medical centers.

- *Specific*

1. To describe the demographic and clinical characteristics of patients with a diagnosis of placenta accreta spectrum.
2. To analyze the clinical outcomes of patients diagnosed with placenta accreta spectrum according to the topographic classification.
3. To explore the acceptability of the topographic classification for placenta accreta spectrum among obstetrician-gynecologists at the participating medical centers.

EXPECTED RESULTS

The aim of this study is to describe the demographic and clinical characteristics of patients with a diagnosis of placenta accreta spectrum, and to determine the correlation between the topographic classification and the clinical outcomes found in the study. Finally, to evaluate whether the proposed classification is accepted by the obstetrician-gynecologists of the participating centers that manage placenta accreta spectrum patients.

METHODOLOGY

Design:

1. Multicentric study of a prospective cohort.

It is clarified that this is an observational study, in which data will be obtained from the medical records and other documents in each participating center, which are considered to be of routine use in day-to-day clinical practice. The study of the outcomes proposed in this protocol will be limited to those recorded in the clinical records and will be taken into account until the participant is discharged

from the hospital, during which a surgical intervention was performed due to the suspicion or diagnosis of PAS.

Study population:

1. Pregnant patients with a diagnosis of placenta accreta spectrum who visits any of the participating medical centers.
2. Obstetrician-gynecologists working in participating medical centers.

Participating centers:

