In both cases, the null hypothesis (H_0) indicates that the mean or median numbers of the 7 subpopulations are equal; the alternate hypothesis (H_a) refers to the above being different. If the p-value indicated by those tests is ≥ 0.05 (5%), it can be stated that there are no statistically significant differences between the mean or median numbers of the 7 subpopulations, with 95% confidence, which is set for the study. If the p-value is < 0.05 , the hypothesis of having no difference in the mean or median numbers (H_0) is rejected. That does not imply that a particular subgroup is superior or inferior to another.

For qualitative variables, a statistical test of the difference in proportions of the 7 subgroups (independent groups) will be performed by means of the Chi-square test. A result with a p-value ≥ 0.05 (5%) can be interpreted as: the proportions of the variable in question do not differ, in terms of statistical significance, among the seven groups. In case the p-value is < 0.05 indicates that there are statistically significant differences between at least two of the seven groups with respect to the proportions of the variable addressed. This does not imply that a particular subgroup is superior or inferior to another.

The results are shown in Table 3.

Specific Objective 2: To analyze the clinical outcomes of patients diagnosed with placenta accreta spectrum according to anatomical classification.

Descriptive Analysis: Stratification by subgroups will be performed according to the anatomical classification of PAD as follows: T1, T2a, T2b, T3, T4, T5a and T5b. Qualitative variables will be summarized as percentages and presented as absolute frequencies. For quantitative variables, the normality distribution will be determined by means of the Kolmogorov statistic.

Smirnov (sample size greater than 50 patients is expected), where a result of p-value >0.05 would comply with the assumption of normality. For variables with normal distribution, mean and standard deviation will be determined; and for variables without normal distribution, median and interquartile ranges (Q1 - Q3) will be indicated.

Inferential Analysis: For quantitative variables, a statistical test of the difference in means of the 7 subgroups (independent groups) will be performed by means of one-way ANOVA for independent groups. If the variable does not have a normal distribution, the Kruskal-Wallis test will be performed.

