In both cases, the null hypothesis (H_0) indicates that the means or medians of the 7 subpopulations are equal; the alternate hypothesis (H_a) refers to the above being different. If the p-value indicated by these tests is ≥ 0.05 (5%), it can be stated that there are no statistically significant differences between the means or medians of the 7 subpopulations, with 95% confidence, which is set for the investigation. If the p-value is < 0.05 , the hypothesis of equality of population means or medians (H_0) is rejected. This does not imply that a particular subgroup is superior or inferior to another.

For qualitative variables, a statistical test of the difference in proportions of the 7 subgroups (independent groups) will be performed by means of the Chi-square test. A result with a p-value ≥ 0.05 (5%) can be interpreted as: the proportions of the variable in question do not differ in terms of statistical significance, among the seven groups. In case the p-value is < 0.05 , it indicates that there are statistically significant differences between at least two of the seven groups with respect to the proportions of the variable been assessed. That does not imply that a particular subgroup is superior or inferior to another.

The results are shown in Table 4.

Specific Objective 3: To explore the acceptability of the topographic classification of

placenta accreta spectrum among obstetrician-gynecologists at the participating medical centers.

In the scientific literature there is no validated scale to evaluate the acceptability of a new clinical classification, which in this case is proposed as a topographic classification of PAS. After an exhaustive search, it was concluded that the *The Ottawa Acceptability of Decision Rules Instrument* would be utilized, which is a widely used instrument to evaluate the acceptability of a norm among physicians. There is no linguistic adaptation to Spanish, so a direct translation of its content was made.

After the principal investigator had reviewed it, was necessary make adaptations to some items, which were:

- a) Change the original term "norm" to "*anatomical classification for PAS*". In all items.

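### Objective 2 promises to relate topographic type to clinical outcomes, but its only inferential output is an omnibus p-value, so the strength of the association and its uncertainty are never estimated

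*Combined protocol and SAP*

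**What the plan says.** The Research Question is "Is the topographic classification of placenta accreta spectrum useful in determining possible clinical outcomes", and the Research Hypotheses answer it in the affirmative: "The topographic classification of placenta accreta spectrum is useful in determining possible clinical outcomes". The Theoretical Framework (Topographic classification) calls for a prospective multicentre study that "assesses its validity and correlation to surgical difficulty and" clinical outcomes. Expected Results repeats the aim: "to determine the correlation between the topographic classification and the clinical outcomes found in the study".

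Under Data Management and Statistical Analysis, Specific Objective 2 has two parts.

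- **Descriptive.** Counts with percentages, or mean (SD) or median (quartiles), by type.
- **Inferential.** For quantitative outcomes, "one-way ANOVA for independent groups. If the variable does not have a normal distribution, the Kruskal-Wallis test will be performed". For qualitative outcomes, "a statistical test of the difference in proportions of the 7 subgroups (independent groups) will be performed by means of the Chi-square test".

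A p-value below 0.05 is read narrowly: "it indicates that there are statistically significant differences between at least two of the seven groups". The plan adds: "That does not imply that a particular subgroup is superior or inferior to another".

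Blank Table 4 has one column per type and a single p-value column. Operational Aspects ties the analysis to the table of variables and the blank tables. Neither the text nor the tables include a confidence interval, a contrast between types, a correlation or other association measure, or a statement of what would count as useful.

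**The concern.** The aim is a question of size: how strongly is type related to outcome, and how precisely is that known? An omnibus test answers a different question, namely whether the data are compatible with no difference anywhere among seven groups. Its p-value mixes strength of association with number of women, and the plan correctly declines to read any ordering of types into it.

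The descriptive columns show point estimates without any sign of their precision. That matters because recruitment aims for as few as 9 women in the rarest type. Bare percentages from such a group would look far firmer than they are. The protocol hopes that confirming usefulness will spread the classification internationally, so the basis for that conclusion should be an estimate with its uncertainty.

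**Working it through.** **1. The minimum of 9 per type (Sample size and sampling strategy).** Inputs: p₁ = 0.3105, p₂ = 0.9999, two-sided 5%, power 80%, ratio 1.

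- Mean p̄ = 0.6552; difference d = 0.6894.
- Fleiss: n = [1.96·√(2p̄(1−p̄)) + 0.842·√(p₁(1−p₁) + p₂(1−p₂))]² / d² = 6.13, rounded up to 7.
- With continuity correction: (6.13/4)·[1 + √(1 + 4/(6.13 × 0.6894))]² = 8.79, rounded up to 9.

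Both match the plan's output. The figure is not in dispute; it is used here only as the smallest group the plan aims for.

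**2. Precision at 9 women.** Wilson interval: [p + z²/2n ± z·√(p(1−p)/n + z²/4n²)] / (1 + z²/n). For 5 of 9: (0.5556 + 0.2134 ± 1.96 × 0.1982)/1.4268 = 0.539 ± 0.272, or 27% to 81%. The 5 is an assumed count. At the extreme of 9 of 9 the interval is 70% to 100%.

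**3. The plan's source table.** The section gives four types with percentages. Event counts are back-calculated by multiplying each percentage by n.

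| Type | n | Complications | Risk |
|---|---|---|---|
| T1 | 248 | 77 | 31.05% |
| T2 | 44 | 22 | 50% |
| T3 | 23 | 22 | 95.65% |
| T4 | 11 | 11 | 100% |
| All | 326 | 132 | 40.5% |

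- **Chi-square** = Σ nᵢ(pᵢ − p)² / [p(1−p)] = (2.211 + 0.398 + 6.998 + 3.895)/0.24096 = 56.0 on 3 df; p = 4.1 × 10⁻¹².
- **Cramer's V** = √(56.04/326) = 0.41 (bootstrap 95% CI 0.34 to 0.49).
- **Share of complications in T1** = 77/132 = 58%.
- **c-statistic**, types ordered T1 to T4. Non-events are 171, 22, 1 and 0. Concordant pairs: 22×171 + 22×193 + 11×194 = 10,142. Tied pairs: 77×171 + 22×22 + 22×1 + 0 = 13,673. c = (10,142 + 6,836.5)/(132 × 194) = 0.66 (bootstrap 95% CI 0.61 to 0.71).

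**4. Same association, different sample size.** Shrinking the table in proportion multiplies chi-square by N/326 and leaves every risk, V and c unchanged.

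| N | Chi-square (3 df) | p | V |
|---|---|---|---|
| 63 | 10.8 | 0.013 | 0.41 |
| 100 | 17.2 | 0.0006 | 0.41 |
| 326 | 56.0 | 4.1 × 10⁻¹² | 0.41 |

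The p-value changes by nine to ten orders of magnitude while the strength of association stays fixed.

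**5. What intervals would add.** Differences in risk from T1, with Newcombe 95% intervals built from the Wilson limits of each pair:

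- T2: 50.0 − 31.0 = 19 points (4 to 34)
- T3: 95.7 − 31.0 = 65 points (47 to 71)
- T4: 100 − 31.0 = 69 points (42 to 74)

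These show that T3 and T4 are clearly separated from T1, while the T2 difference could be anywhere from slight to large. One p-value of 4.1 × 10⁻¹² shows neither.

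**The case against.** The strongest reply is that the plan is descriptive and does not overreach. Risk by type is planned in Table 4, so a reader can see a gradient and subtract one column from another. The objectives are worded as evaluating and analysing outcomes by type, which does not promise individual prediction. The plan also limits what p < 0.05 may be taken to mean. All of this stands, and it rules out four stronger readings that a reader might infer.

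- **That only p-values are reported.** Not so: estimates by type are tabulated. What is missing is their uncertainty, the contrasts and a measure of association.
- **That p < 0.05 will be declared to mean useful.** No passage says this, and the plan's caution points the other way. The gap is that no other basis for the conclusion is given.
- **That association with outcome goes untested.** The omnibus tests do test it; they do not measure it.
- **That type predicts poorly.** The source table does not show this. T3 and T4 together have 33/34 = 97% complications against 31% in T1. The c-statistic is 0.66 largely because T1 is 248/326 = 76% of the sample; the same four risks with equal group sizes give 0.87. A c-statistic therefore reflects referral mix as well as the classification, and the documents offer no cut-off for it.

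The reply leaves one gap open. Subtracting columns gives a difference with no interval, which in a type with about nine women is not interpretable.

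**Conclusion.** The point holds in this form: the plan states an aim of relating type to outcome, and provides a test of no difference but no estimate of how strong the relation is or how uncertain. By its own wording the planned inference cannot say which types do better or worse. The consequence is an incomplete answer to the main question rather than a wrong one, and it is easily repaired before analysis.

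Size: with 9 women, a risk near one half carries an interval about 54 percentage points wide (27% to 81%). In the source table, p runs from 0.013 to 4.1 × 10⁻¹² for one and the same V of 0.41, according to sample size alone.

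Assumptions: the illustration uses four types from one retrospective source, not this study's seven. Counts are back-calculated from percentages, and the source's definition of total complications is not given. The values show that the p-value does not convey strength; they do not forecast this study's results.

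**What to change.** In Specific Objective 2 and Table 4, for two outcomes, any complication (variable 25, Clavien-Dindo above None) and intraoperative blood loss (variable 16):

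1. Report the risk, or the mean or median, by type with a 95% CI (Wilson or exact for proportions), and the difference from T1 with a 95% CI.
2. Report one measure of association with a 95% CI: for example Cramer's V for any complication, and the share of variance explained (eta-squared or its rank version) for blood loss. Prefer bias-corrected forms. With seven types and no association, chi-square averages 6, so at an assumed 100 women the raw V would be about √(6/100) = 0.24.
3. State that the conclusion rests on these estimates, with the omnibus p-value as support.

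Table 4 needs two rows for this: its complications block starts at Grade I, and it lists haemorrhage stages but no blood-loss volume. Cramer's V needs no ordering of the types.

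A c-statistic may be added as a secondary description, with a note that it depends on case mix. No c-statistic cut-off should define usefulness.

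Cost: a paragraph of plan wording and a little more analysis, on variables already collected. The rare types will show wide intervals, which is an accurate picture of what the study can say about them.
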